6 STUDY OBJECTIVES

[figure not shown]
6.1 Primary Objective(s)

[figure not shown]
Table 6–1 Primary Objective(s)

Objective(s)	Endpoint(s)
To evaluate binocular visual acuity at distance of LID233309 lenses and Oasis MF lenses.	Binocular HC/HI VA (logMAR) at distance (4 m) at Week 1

6.2 Secondary Objective(s)

Not Applicable

6.4 Safety Objective(s)

Table 6–3 Safety Objective(s)

Objective(s)	Endpoint(s)
To describe the safety profile of the study products.	
• Adverse events• Biomicroscopy findings• Device deficiencies

7 INVESTIGATIONAL PLAN

7.1 Study Design

[figure not shown]
This is a prospective, randomized, bilateral, crossover, double-masked (study lenses), dispensing, multicenter study comparing the LID233309 lenses and Oasys MF contact lenses.

Subjects will be randomized [REDACTED] and exposed to both test and comparator lenses for bilateral wear. Subjects will be expected to attend 7 office visits and will be dispensed study lenses (test and comparator lenses) for a 14-day duration of bilateral wear each (total of approximately 28 days of lens wear). Between Visits 1 and 2, a washout period (wearing spectacles) of 2 [at least 48 hours] - 4 days after the end of Visit 1 will be required, and between Visits 4 and 5, a washout period (wearing spectacles) of 2 [at least 48 hours] - 4 days after the end of Visit 4 will be required. Subjects will be expected to wear their study contact lenses for at least 10 hours per day, over a 14-day period per study lens. Subjects will be asked to wear study lenses for 16 hours on the days prior to each Follow-up Visit (Visit 3, 4, 6 & 7).

In this trial, as both test and comparator lenses have manufacture specific fitting guides, the PI may become aware of the identity of the lens during fitting. However, the PI must remain masked to the complete randomized sequence which includes study lenses. The investigator will be masked to the dispensed study lenses. The subjects will be masked to both fitting and dispensed study lenses. An unmasked site coordinator will prepare the lenses for both lens fitting and dispensing.

All study contact lenses will be prescribed according to the subject's prescription. CLEAR CARE Cleaning & Disinfecting Solution will be provided for use during the duration of the study.

Figure 7-1 Study Design

7.2 Rationale for Study Design

This study design is justified based upon an evaluation of the results of relevant preclinical and clinical testing, as described within the IB.

The bilateral, crossover study design will ensure that the same subject is exposed to both the test and comparator lens materials during the study visits and wearing period; therefore, [REDACTED] assessments can be obtained for both lenses from the same subject.

The study will include only those subjects who are successful wearers of soft multifocal contact lenses in both eyes during the past 6 months for a minimum of 5 days per week and 10 hours per day. This will avoid confounding safety responses in nonadapted subjects. The study will exclude subjects who are habitual Oasys MF contact lens wearers, daily disposable contact lens wearers and monovision contact lens, and wearers of contact lens in 1 eye only.

Lubrication/rewetting drops will not be permitted during study lens wear or at study visits, as this may confound the primary effectiveness and key exploratory variables. However, habitual lubrication/rewetting drop usage is allowed up to 10 minutes prior to lens insertion and any time after lens removal during the study.

Currently pregnant or lactating women and participants with any history of amblyopia, strabismus or binocular vision abnormalities will be excluded from the trial to prevent confounding the safety/effectiveness endpoints. Subjects who become pregnant during the study will not be discontinued; however, data will be excluded from the effectiveness analyses because pregnancy can alter refraction and visual acuity results.

7.3 Rationale for Duration of Treatment/Follow-Up

Subjects will wear each study product bilaterally for their respective wear cycles on a daily wear modality. The wear cycle for the LID233309 contact lens is 7 days, and that for the

marketed Oasys MF contact lens is 14 days. [REDACTED]

7.4 Rationale for Choice of Comparator Product

[figure not shown]
The Oasys MF contact lenses have been chosen as the comparator product because these lenses have a comparable wear modality and same indication for correction of presbyopia.

7.5 Data Monitoring Committee

Not applicable.

8 STUDY POPULATION

The study population consists of volunteer subjects, of at least 40 years of age who are habitual biweekly or monthly soft multifocal contact lens wearers have at least 6 months of contact lens wearing experience, and who wear their habitual lenses at least 5 days per week and at least 10 hours per day. It is aimed to enroll (consent) approximately 96 subjects in approximately 8 sites in the United States, with a target of 92 total subjects completed, with 7 (intended minimum) to 16 (intended maximum) subjects per site. Site-specific targets may vary based upon individual site capabilities. Estimated time needed to recruit subjects for the study is approximately 5 weeks; however, unanticipated circumstances may shorten or lengthen this time and would not require amendment of this protocol.

This protocol allows enrollment of the following vulnerable population(s), with associated justification for each population:

Elderly – It is appropriate to include elderly subjects in this clinical trial, as Presbyopia and associated gradual loss of accommodation is part of the aging process and worsens with increasing age is common to this population. Multifocal contact lenses are a commonly used correction option for this condition. The contact lens under study is intended to alleviate this condition. It is necessary to include elderly subjects in this clinical trial to gain data regarding the safety and effectiveness of the LID233309 contact lenses in this population.

Elderly subjects will be protected through the informed consent process, which will include any risks specific to the elderly subjects, as well as any specific responsibilities associated with their participation. In addition, an IRB/IEC will review and approve the inclusion of elderly subjects in this clinical trial prior to enrollment of elderly subjects. Any specific requirements imposed by the IRB/IEC regarding participation of elderly subjects will be implemented and documented, as appropriate. Upon conclusion of the clinical trial, all subjects, including elderly subjects, will return to standard medical care for ongoing conditions.

8.1 Inclusion Criteria

Written informed consent must be obtained before any study specific assessment is performed. Upon signing informed consent, the subject is considered enrolled in the study.

Subjects eligible for inclusion in this study must fulfill **all** of the following criteria:

1. Subject must be able to understand and sign an IRB/IEC approved informed consent form.
2. Subject must be willing and able to attend all scheduled study visits as required per protocol.
3. Subject must be at least 40 years of age.
4. Subject must be willing to stop wearing their habitual contact lenses for the duration of study participation.

5. Current wearer of biweekly/monthly replacement multifocal soft contact lenses in both eyes for a minimum of 5 days per week and 10 hours per day during the past 6 months.
6. Manifest cylinder ≤ 0.75 D in each eye.
7. BCVA distance (as determined by manifest refraction at screening) 0.1 logMAR or better in each eye.
8. Subject must be able to wear contact lenses within a range of -0.50 D to -4.00 D in 0.25 D steps, -5.00 D, -6.00 D & -8.00 D, +1.00 D to +3.00 D (in 0.25 D steps) +5.00 D and +6.00 D and requiring a near ADD of +0.75 D to +2.50 D in each eye.
9. Subject must be willing to wear the study contact lenses as defined for the full duration of the study.
10. Subject must possess spectacles and be willing to wear habitual spectacles for vision correction when study lenses are not worn, as needed.
11. Subject must be willing to not use readers while wearing study contact lenses for duration of the study.
12. Subject must be willing to wear contact lenses for at least 16 hours per day on the day prior to week 1 and week 2 follow-up visits for both test and comparator lenses.
13. Subject must be willing to NOT use rewetting/lubricating drops at any time during study lens wear.

8.2 Exclusion Criteria

Subjects fulfilling **any** of the following criteria are not eligible for participation in this study.

1. Currently pregnant or lactating, as stated at Screening.
2. Any anterior segment infection, inflammation, or abnormality or disease (including systemic) that contraindicates contact lens wear, as determined by the Investigator.
3. Any use of systemic or ocular medications for which contact lens wear could be contraindicated, as determined by the Investigator.
4. History of refractive surgery or planning to have refractive surgery during the study, or irregular cornea in either eye.
5. Ocular or intraocular surgery (excluding placement of punctal plugs) within the previous 12 months or planned during the study.

6. Biomicroscopy findings at screening that are moderate (Grade 3) or higher and/or corneal vascularization that is mild (Grade 2) or higher, and/or any infiltrate.
7. Current or history of pathologically dry eye in either eye that, in the opinion of the Investigator, would preclude contact lens wear.
8. Current or history of herpetic keratitis in either eye.
9. Eye injury in either eye within 12 weeks immediately prior to enrollment for this trial.
10. Current or history of intolerance, hypersensitivity, or allergy to any component of the study products.
11. Any history of amblyopia, strabismus, or binocular vision abnormalities.
12. Any use of topical ocular medications and artificial tear or rewetting drops that would require instillation during contact lens wear.
13. Habitual Oasys MF contact lens wearers and daily disposable contact lens wearers.
14. The Investigator, his/her staff, family members of the Investigator, family members of the Investigator's staff, or individuals living in the households of the aforementioned persons may not participate in the study.
15. Participation of the subject in a clinical trial within the previous 15 days or currently enrolled in any clinical trial.
16. Monovision contact lens wearers and wearers of contact lens in 1 eye only.
■ [REDACTED]
■ [REDACTED]
18. Wearing habitual contact lenses in an extended wear modality (routinely sleeping in lenses for at least 1 night per week) over the last 6 months prior to enrollment.

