5 INTRODUCTION

5.1 Rationale and Background

Presbyopia is a refractive error condition that develops as part of normal aging in which the natural crystalline lens of the eye progressively loses the focusing ability, resulting in difficulty at focusing for close objects and for activities like reading. The signs of presbyopia become noticeable around the age of 40 years. Presbyopia could be corrected with single-vision, bifocal or progressive spectacles, progressive addition lenses, monovision contact lenses or multifocal contact lenses.

To address the growing needs of presbyopic population, LID233309 soft contact lenses, a new weekly replacement water gradient contact lens has been developed. These multifocal lenses use the center-near aspheric Unique Precision Profile[®] Multifocal design, which has been successfully adopted for DAILIES[®] Total1[®] MF, DAILIES[®] AquaComfort[®] Plus MF, and AIR OPTIX[®] plus HydraGlyde[®] MF contact lenses.

LID233309 soft contact lenses are indicated for the optical correction of presbyopia, with or without refractive ametropia (myopia and hyperopia) in persons with nondiseased eyes. The lenses are to be used for daily wear with removal for disposal, or cleaning and disinfection (chemical, not heat) prior to reinsertion, as recommended by the eye care professional. Lenses should be discarded and replaced with a new pair each week or more often, if recommended by an eye care professional.

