3 SUBJECT CHARACTERISTICS AND STUDY CONDUCT SUMMARIES

[REDACTED]

[REDACTED]

[REDACTED]

[REDACTED]

[REDACTED]

The following tables will be presented:

- Subject Disposition by Lens Sequence
- Subject Disposition by Study Lens Sequence
- Analysis Sets by Study Lens
- Analysis Sets by Study Lens Sequence
- Subject Accounting by Lens
- Subject Accounting by Study Lens Sequence
- Demographics by Lens Sequence
- Demographics by Study Lens Sequence
- Baseline Characteristics by Study Lens Sequence [lens brand; hours of digital device use per day; pupil size]

Subject accounting and demographics tables will be summarized on the safety, full, and per protocol analysis datasets. Baseline characteristics will be summarized on the full and per protocol analysis datasets.

In addition, the following subject listings will be provided:

- Listing of Subjects Excluded from Protocol Defined Analysis Sets
- Listing of Lens Sequence Assignment by Investigator
- Listing of Subjects Discontinued from Study

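### Should habitual wearers of lenses sharing the test lens's optical design be excluded or analysed separately?

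*Protocol*

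**What the plan says.** Protocol Section 8.1 admits any "Current wearer of biweekly/monthly replacement multifocal soft contact lenses in both eyes", subject to wearing-time minimums over the past 6 months and with no brand restriction. Section 8.2, exclusion 13, removes "Habitual Oasys MF contact lens wearers and daily disposable contact lens wearers". The design rationale in Section 7.2 repeats the rule: "The study will exclude subjects who are habitual Oasys MF contact lens wearers, daily disposable contact lens wearers and monovision contact lens", together with one-eye wearers. The item between exclusions 16 and 18 is blacked out.

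On the optics, Section 5.1 states: "These multifocal lenses use the center-near aspheric Unique Precision Profile[®] Multifocal design". It names three marketed lenses that already use the design: two sold under the DAILIES name, and "AIR OPTIX[®] plus HydraGlyde[®] MF contact lenses". It gives no replacement schedule for the third.

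Habitual brand is recorded at Visit 1 (Protocol Table 3-1 and Section 10.2.7). SAP Section 3 plans a table titled "Baseline Characteristics by Study Lens Sequence [lens brand; hours of digital device use per day; pupil size" on the full and per protocol sets. SAP Section 4.3 describes the primary analysis as summary statistics with a two-sided 95% confidence interval at Week 1, and likewise at Dispense and Week 2. SAP Section 4.2 formulates no hypothesis, and the SAP executive summary says that success criteria do not apply. Several lines of SAP Section 4 and the title of 4.5 are redacted.

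**The concern.** The visible eligibility text is one-sided. People who chose the comparator lens are kept out. People who chose a reusable lens with the test lens's optics are not visibly kept out. Entrants must also be established multifocal wearers, so some could have been selected for tolerating the test design.

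A crossover does not cure this. Randomizing the order balances period effects, but an advantage that travels with the lens appears in the test-minus-comparator difference in both sequences. A spectacle washout of 2 to 4 days does not reverse selection for tolerance of a design. A brand table by sequence shows whether the sequences are alike, not whether the lens effect depends on the habitual design. If a reader set the two lens means side by side, part of any gap in favour of the test lens might reflect prior adaptation.

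**Working it through.** **1. The plan's own figure.** Inputs from SAP Section 7: n = 92, SD = 0.12, 95% two-sided interval, coverage probability 0.85.

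- Plain half-width: t(0.975; 91) × SD / √n = 1.986 × 0.12 / √92 = 0.0249.
- At the 85th percentile of the sample SD, multiply by √(χ²(0.85; 91) / 91), about 1.074: 0.0267, which rounds to the stated 0.027.

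This is the precision of a mean for one lens.

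**2. Size of the possible shift.** Let p be the share of same-design habitual wearers and d their extra advantage on the test lens. The lens difference moves by p × d. Both inputs are assumptions.

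| p | d (logMAR) | p × d | Divided by 0.027 |
|---|---|---|---|
| 0.10 | 0.02 | 0.002 | 0.07 |
| 0.25 | 0.04 | 0.010 | 0.37 |
| 0.50 | 0.04 | 0.020 | 0.74 |
| 0.50 | 0.06 | 0.030 | 1.11 |

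For the shift to equal 0.027, d must be 0.027 / p: 0.27 at p = 0.10, 0.108 at p = 0.25, 0.054 at p = 0.50 and 0.036 at p = 0.75. At d = 0.05, p must reach 0.027 / 0.05 = 0.54.

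**3. Is 0.027 the right yardstick?** Not for a difference. With within-subject correlation ρ (not in the documents), the SD of the difference is 0.12 × √(2(1 − ρ)), and the plain t half-width at n = 92 is:

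- ρ = 0.3: SD 0.142, half-width 0.0294
- ρ = 0.5: SD 0.120, half-width 0.0249
- ρ = 0.7: SD 0.093, half-width 0.0192

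The same shift could weigh somewhat more or less than the table suggests.

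**4. What a split by habitual design would show.** Half-widths for a single-lens mean within each group, by the method of step 1:

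| p | Same design (n) | Other (n) |
|---|---|---|
| 0.10 | 0.113 (9) | 0.028 (83) |
| 0.25 | 0.059 (23) | 0.031 (69) |
| 0.50 | 0.039 (46) | 0.039 (46) |

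The quantity of interest, d, is the between-group contrast in within-subject differences. Its plain half-width is 1.986 × SD of difference × √(1/n₁ + 1/n₂):

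- 23 versus 69: 0.068, 0.057 and 0.045 for ρ = 0.3, 0.5 and 0.7
- 46 versus 46: 0.059, 0.050 and 0.039 for the same values

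For d between 0.02 and 0.05, the table would usually leave the question open. Only a high correlation combined with the top of that range would give an interval clear of zero on average.

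**5. The eligibility texts compared.** Of the three lenses named in Section 5.1, the two DAILIES lenses are taken to fall under the daily-disposable exclusion. The argument then rests on one lens, and it needs two things the documents do not show: that the lens is replaced biweekly or monthly, and that the redacted exclusion does not cover it. The reverse claim, that nobody enrolled is adapted to optics like the comparator's, also lacks support. Exclusion 13 names a product, and nothing is said about which other lenses resemble it. Section 7.2 asks for success with soft multifocals, not with one brand.

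**The case for a change.** The best argument for a change is that the protocol itself treats adaptation as relevant. Section 7.2 restricts entry to successful multifocal wearers so that unadapted subjects do not confound safety responses, and Section 11.3 refers to an adaptation period for lens awareness and visual changes. Section 7.1 describes the study as comparing two lenses, and Section 5.2 says that it serves product development. The means will therefore be read together whether or not a test is planned. Brand is already collected, one more table costs little, and a split fixed before unmasking is more credible than one chosen afterwards.

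Much of this stands. The visible criteria are asymmetric, no visible effectiveness summary is split by habitual design, and the crossover does not cancel the effect. It does not show that the plan's stated output is wrong. The mean for each lens in the enrolled population is a legitimate descriptive target, and its interval estimates that target. The shift becomes a bias only if the gap between means is read as a contrast in people adapted to neither design, and the visible plan makes no such inference. Requiring a comparative statement to hold among other-brand wearers would add a decision rule to a study that has none. Some asymmetry is also unavoidable: an investigational lens has no habitual wearers to exclude, and barring everyone who shares its optics would cost recruitment and narrow the population.

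**Conclusion.** No change to the plan is needed. The asymmetry is visible, but its effect cannot be sized from the documents: assumed inputs give anything from a negligible 0.002 to 0.030 logMAR, and 0.027 is reached only with a large share of same-design wearers, a large advantage, or both. That range depends on an unstated replacement schedule and on redacted text containing nothing that settles the matter. The planned per-lens summaries remain sound for a descriptive study, and the baseline brand table lets a reader see how many subjects wore a same-design lens. If that share proves large, an analyst can add a descriptive Week 1 summary by habitual design, noting its wide intervals. The eligibility rule is a fair trade-off, and neither an eligibility change nor a decision rule is warranted.

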8.3 Rescreening of Subjects

Rescreening of subjects is not allowed in this study.

9 TREATMENTS ADMINISTERED

9.1 Investigational Product(s)

Test Product(s): LID233309

Comparator Product(s) (If applicable): Oasys MF

Table 9–1 Test Product

Test Product	Serafilcon A Multifocal contact lenses (LID233309)
Manufacturer	Alcon Laboratories, Inc. [name] USA
Indication for use and intended purpose in the current study	The investigational frequent replacement multifocal contact lens is indicated for the optical correction of presbyopia with or without refractive ametropia (myopia and hyperopia) persons with nondiseased eyes. The lenses are intended for daily wear (less than 24 hours while awake), with removal for cleaning and disinfection (chemical, not heat) prior to reinsertion.
Product description and parameters available for this study	
 • Material: Serafilcon A • Water content: 55% 
Power range: Limited lens parameters will be available for use in this study:
 
 ○ -0.50 D to -4.00 D in 0.25 D steps, -5.00 D, -6.00 D, and -8.00 D with ADD of LO, MED, or HI (as available) ○ +1.00 D to +3.00 D in 0.25 D steps, +5.00 D and +6.00 D with ADD of LO, MED, or HI (as available) 
 • Base curve (mm): 8.4 (Target) • Diameter (mm): 14.2 (Target)
Formulation	Refer to IB
Usage	
 • Wear: 
 ○ Daily Wear

	
 ○ Bilateral ● Replacement period: 
 ○ Replaced weekly for ~14 days ○ The unmasked staff must maintain the subject and investigator masking to the study product being used. ● Exposure: Study lenses are to be worn during typical contact lens wearing hours, on all days during the study lens wearing period, at least 10 hours per day, over each wear cycle (7 days [-0/+1] according to randomization assignment). Subjects will be asked to wear their study lenses for 16 hours on the days prior to each Follow-up Visit (Visit 3, 4, 6, & 7). ● Lens Care: Cleaned and disinfected with CLEAR CARE Cleaning & Disinfecting Solution after each use ● Replacement lenses will not be provided to the subject. In the event a lens needs to be replaced, the subject must return to the site for a replacement lens. Until the replacement lens is obtained, the subject must store the study lenses as instructed. Refer to MOP for detailed instructions.

Number/Amount of product to be provided to the subject
	
Subjects will be provided a pair of test lenses at the applicable visit as per randomization. Lenses (to be used for fitting and study lens wear) will be provided in bulk by the sponsor before the start of the trial. (Any additional lenses needed can be requested by the site to the sponsor).

Packaging description
	
Blister foil pack

Labeling description
	
 ● Lens foil label includes: 
 ○ material name and identifier ○ base curve ○ diameter ○ manufacturing protocol number (for the following parameters: -0.50 HI, -0.75 HI, +1.00 HI, +1.25 HI, +1.50 HI) ○ packing solution ○ power ○ lot number ○ expiration date

	
 ○ content statement ○ investigational device statement ○ sponsor information 
 ● Lens inventory will be provided in packages and identified with the following: 
 ○ a color-coded label stating the study protocol number ○ LID Number ○ power ○ an investigational use only statement ○ handling unit/tracking number
Training and/or experience requirements for device	No additional training or experience is required to administer the test product.
Storage conditions	Lenses are to be stored at room temperature
Additional information	N/A
Supply	
 ● Lenses will be provided in bulk by the sponsor ● CLEAR CARE Cleaning & Disinfecting Solution supplied by sponsor to be provided to the subject ● LacriPure saline will be permitted for rinsing the lens(es) after removal and prior to insertion, if required 
Refer to the MOP for a detailed description

Table 9–2 Comparator Product

Comparator Product(s)	ACUVUE® OASYS MULTIFOCAL with PUPIL OPTIMIZED DESIGN (Oasys MF) contact lenses (senofilcon A)
Manufacturer	Johnson & Johnson
Indication for Use	These comparator multifocal soft contact lenses are indicated for the optical correction of presbyopia, with or without refractive ametropia (myopia and hyperopia) in phakic or aphakic persons with nondiseased eyes.

[figure not shown]
Product description and parameters available for this study	
Commercial description for Product:
 
• Material: Senofilcon A• Water content: 38%• Base curve (mm): 8.4 mm• Diameter (mm): 14.3 mm 
Power range: Limited lens parameters will be available for use in this study:
 
○ -0.50 D to -4.25 D in 0.25 D steps, -5.25 D, -6.25 D, and -8.25 D with ADD of LO, MID, or HI (as available)○ +0.75 D to +3.00 D in 0.25 D steps, +4.75 D and +5.75 D with ADD of LO, MID, or HI (as available)
Formulation	Refer to package insert
Usage	
• Wear:
○ Daily wear○ Bilateral• Replacement period:
○ Replaced biweekly for ~14 days○ The unmasked staff must maintain the subject and investigator masking to the study product being used• Exposure: Study lenses are to be worn during typical contact lens wearing hours, on all days during the study lens wearing period, at least 10 hours per day, over the wear cycle (total ~14 days of 7 days [-0/+1] in each follow-up, according to randomization assignment). Subjects will be asked to wear their study lenses for 16 hours on the days prior to each Follow-up Visit (Visit 3, 4, 6, & 7).• Lens Care: Cleaned and disinfected with CLEAR CARE Cleaning & Disinfecting Solution after each use• Replacement lenses will not be provided to the subject. In the event a lens needs to be replaced, the subject must return to the site for a replacement lens. Until the replacement lens is obtained, the subject must store the study lenses as instructed. Refer to MOP for detailed instructions.
Number/Amount of Product to be	Subjects will receive 1 pair of comparator lenses as per randomization, in parameters as determined during trial.

Provided to the subject	
Packaging description	Provided in Commercial Packaging
Labeling description	Commercial foil
Training and/or experience requirements for device	No additional training or experience is required to administer the comparator.
Storage conditions	Lenses are to be stored at room temperature
Additional identifying information	N/A
Supply	
• Each site will procure their own comparator lenses, to be used for lens fitting and study lenses wear• CLEAR CARE Cleaning & Disinfecting Solution supplied by sponsor to be provided to the subject• LacriPure saline will be permitted for rinsing the lens(es) after removal and up to 10 minutes prior to insertion, if required Refer to the MOP for a detailed description

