		Visit 1 Screening/ Baseline/ Lens Fitting	Visit 2 Dispense Lens 1	Visit 3 Week 1 Follow-up Lens 1	Visit 4 Week 2 Follow-up Lens 1	Visit 5 Dispense Lens 2	Visit 6 Week 1 Follow-up Lens 2	Visit 7 Week 2 Follow-up Lens 2/Exit		
Procedure/ Assessment	Pre-screening		Day 1 [Visit 2 must occur after washout with habitual spectacles, 2 (at least 48 hours) - 4 days after the end of Visit 1]	(7 -0/+1 days after Visit 2)	(7 -0/+1 days after Visit 3)	Day 1 [Visit 5 must occur after washout with habitual spectacles, 2 (at least 48 hours) - 4 days after the end of Visit 4]	(7 -0/+1 days after Visit 5)	(7 -0/+1 days after Visit 6)		
██████████ ██████████ ██████████ ██████████										
██████████ ██████████ ██████████		■								
██████████ ██████████		■								
Determine and record study lens power to be dispensed		X								
Dispense study lenses*			X	X		X	X			(X)
██████████ ██████████			■	██████████	■	■	██████████	■	■	■

		Fitting Lens 1 (Fit Period 1) and Fitting Lens 2 (Fit Period 2)	Lens 1 (Period 1)			Lens 2 (Period 2)			Early Exit	Unscheduled Visit
		Visit 1 Screening/ Baseline/ Lens Fitting	Visit 2 Dispense Lens 1	Visit 3 Week 1 Follow-up Lens 1	Visit 4 Week 2 Follow-up Lens 1	Visit 5 Dispense Lens 2	Visit 6 Week 1 Follow-up Lens 2	Visit 7 Week 2 Follow-up Lens 2/Exit		
Procedure/ Assessment	Pre-screening		Day 1 [Visit 2 must occur after washout with habitual spectacles, 2 (at least 48 hours) - 4 days after the end of Visit 1]	(7 -0/+1 days after Visit 2)	(7 -0/+1 days after Visit 3)	Day 1 [Visit 5 must occur after washout with habitual spectacles, 2 (at least 48 hours) - 4 days after the end of Visit 4]	(7 -0/+1 days after Visit 5)	(7 -0/+1 days after Visit 6)		
██████████ ██████████ ██████████ ██████████										
██████████ ██████████ ██████████ ██████████ ██████████ ██████████			■	■ ██████████	■	■	■ ██████████ ██████████	■	■	■
VA (logMAR) with study lenses at • Distance (4 m; OD, OS, OU) ██████████ ██████████			X	X ██████████	X	X	X ██████████ ██████████	X	(X)	(X)

		Fitting Lens 1 (Fit Period 1) and Fitting Lens 2 (Fit Period 2)	Lens 1 (Period 1)			Lens 2 (Period 2)			Early Exit	Unscheduled Visit
		Visit 1 Screening/ Baseline/ Lens Fitting	Visit 2 Dispense Lens 1	Visit 3 Week 1 Follow-up Lens 1	Visit 4 Week 2 Follow-up Lens 1	Visit 5 Dispense Lens 2	Visit 6 Week 1 Follow-up Lens 2	Visit 7 Week 2 Follow-up Lens 2/Exit		

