Procedure/ Assessment	Pre-screening		Day 1 [Visit 2 must occur after washout with habitual spectacles, 2 (at least 48 hours) - 4 days after the end of Visit 1]	(7 -0/+1 days after Visit 2)	(7 -0/+1 days after Visit 3)	Day 1 [Visit 5 must occur after washout with habitual spectacles, 2 (at least 48 hours) - 4 days after the end of Visit 4]	(7 -0/+1 days after Visit 5)	(7 -0/+1 days after Visit 6)		
						(Collect & Review Calendar)			(Collect & Review Calendar)	(Collect & Review Calendar)
				■	■	■	■			■
Collect worn study lenses*				X	X		X	X	X	(X)
								■	■	
AEs			X	X	X	X	X	X	X	X
Device deficiencies			X	X	X	X	X	X	X	X
Exit Form			(X)	(X)	(X)	(X)	(X)	X	X

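### Is there a new comparator pair to measure at Week 1, when the plan supplies only one pair?

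*Protocol*

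**What the plan says.** The product tables in protocol section 9.1 treat the two lenses differently. For the comparator, Table 9-2 has "Subjects will receive 1 pair of comparator lenses as per randomization" and "Replaced biweekly for ~14 days", and gives exposure as "total ~14 days of 7 days [-0/+1] in each follow-up". Section 7.3 agrees: the wear cycle of the "marketed Oasys MF contact lens is 14 days". For the test lens, Table 9-1 has "Replaced weekly for ~14 days" and "Subjects will be provided a pair of test lenses at the applicable visit as per randomization".

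The schedules are organised by period (Lens 1, Lens 2), not by product. The row "Dispense study lenses" is ticked at Visits 2, 3, 5 and 6 in both protocol Table 3-1 and SAP Table 10-1. SAP Table 10-1 ticks "Collect worn study lenses" at Visits 3, 4, 6 and 7, and labels the distance acuity entries at Visits 3 and 6 as *Old & New*. None of these entries is limited to one lens.

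The primary endpoint is binocular distance acuity at Week 1, summarised descriptively with a 95% confidence interval. Dispense and Week 2 are summarised the same way (protocol 12.4.1.2, SAP 4.3).

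**The concern.** In a crossover, either Visit 3 or Visit 6 is each subject's comparator Week 1 visit. If the subject has one comparator pair for the whole period, nothing new can be dispensed then, and a *New* acuity reading has no obvious meaning. If instead each tick means a fresh pair, the comparator is changed weekly, which is not what Table 9-2 and section 7.3 describe.

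Sites that followed different passages would measure the comparator at different lens ages at Week 2. The readable endpoint text also does not say which of two Week 1 readings is the primary one. In a purely descriptive study the reported means are the result, so a reader needs to know which lens state they describe.

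**Working it through.** **Pairs implied by the product tables.** Pairs = wear days / replacement cycle.
- Test: 14 / 7 = 2 pairs.
- Comparator: 14 / 14 = 1 pair, which reproduces Table 9-2.

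The schedule has two dispensing ticks per period. That fits two test pairs. For the comparator it fits either one pair handed out twice or two pairs, because the tick gives no count.

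**Visits affected.** 92 completers x 2 periods = 184 Week 1 visits, of which 92 are comparator visits. This only restates that each completer wears the comparator once.

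**Lens age, using the windows of 7 -0/+1 days between visits.**

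| Reading | Test | Comparator, one pair | Comparator, fresh pair at each tick |
|---|---|---|---|
| Week 1, worn pair | 7-8 d | 7-8 d | 7-8 d |
| Week 1, new pair | 0 d | none | 0 d |
| Week 2 | 7-8 d | (7 to 8) + (7 to 8) = 14-16 d | 7-8 d |

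Comparator minus test at Week 2:
- one pair: from 14 - 8 = 6 days to 16 - 7 = 9 days;
- fresh pair at each tick: from 7 - 8 = -1 day to 8 - 7 = +1 day.

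The worn-pair row at Week 1 is the same on both readings.

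**Precision (protocol 12.8, SAP section 7).** Inputs: n = 92, SD 0.12, probability 0.85.
- Half-width at the assumed SD: t(0.975, 91) x 0.12 / sqrt(92) = 1.986 x 0.01251 = 0.0249.
- Multiplied by sqrt(chi2(0.85, 91) / 91), it becomes 0.0267, which rounds to the stated 0.027.

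The figure is reproduced with one reading per subject for a lens mean. It does not depend on how many pairs are dispensed.

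**Why the grid looks as it does.** In both Table 9-1 and Table 9-2 the duty of unmasked staff to protect masking stands under the replacement period itself, and protocol 7.1 has an unmasked coordinator prepare the lenses. Week 1 steps that differed by product would reveal the assignment to the subject and the investigator. Identical steps, with the same comparator pair handed back, fit every explicit statement about the products. The *New* comparator reading is then a second reading on the same pair.

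**What cannot be read.** Text is redacted directly after the wear cycles in section 7.3 and beside the Week 1 acuity ticks in Table 3-1. The row footnotes are not shown. Section numbers jump from 10.2.4 to 10.2.7 and from 10.2.9 to 10.2.13. Details of worn-lens handling are left to the manual of procedures. The SAP contents list starts section 4.1 on page 9 and 4.2 on page 11, but only one sentence of 4.1 is readable. Silence in the public text therefore does not show that the plan lacks a rule.

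**The case for a change.** The strongest case for acting is that no readable sentence says the comparator pair is handed back. Section 10.2.4 has worn lenses collected and returned, with no exception for the comparator. If the pair is reused, *New* means a fresh lens for one product and a repeat reading for the other, and a footnote would settle that cheaply. The asterisk on the dispensing row also marks keratometry and manifest refraction, so it is unlikely to hide a comparator rule.

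Those observations are correct. What they show is a label not explained in the public text. They do not show two explicit instructions in conflict, since the weekly comparator change comes only from reading each tick as a fresh pair.

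The question of which Week 1 reading is primary is similar. The Dispense visit already gives a reading on lenses with no wear, so an analyst without further guidance would naturally take the worn-pair binocular reading for Week 1, one per subject per lens, and report the other separately. That is an inference, and the redacted SAP text may state the choice outright.

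The wording in protocol 12.4.1 that has a binocular endpoint collected for each eye is a separate drafting slip. SAP 4.1 does not repeat it.

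**Conclusion.** No change to the plan follows. This is a gap in the readable wording that staff and analysts can fill sensibly, and text not shown may already fill it. With one comparator pair handed back at Week 1, the product tables and the schedules can both be followed, and the descriptive summaries are sound.

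The worn pair at the primary time point is 7-8 days old for both lenses on either reading. No hypothesis is tested, and the 0.027 half-width stands. What depends on the reading is how the Week 2 comparator summary is described: a pair of 14-16 days, or of 7-8 days if every tick meant a fresh pair. If the unshown text is silent, the Week 1 entries and Table 9-2 should be reconciled as a matter of wording.

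The conclusion assumes that sites follow the explicit product text and that the Week 1 summary uses one binocular reading per subject per lens. It takes no position on which replacement schedule is right.
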